 - Footnote #4 “Infection includes all 75 sites of infection under the INFECTIONS AND INFESTATIONS SOC.” is deleted.
5. [Section 7.1:](#) A section regarding supportive care for pembrolizumab has been added. Subsequent sections have been renumbered.
6. [Section 8.2:](#) A new section for “General Considerations” has been added. Information regarding missed doses and dose delays has been moved to this section. A statement regarding supportive care information has been added to cross reference Sections 7.1 and 8.3a. Subsequent sections have been renumbered.
7. [Section 8.3:](#) The Dose Modification Guidelines for Pembrolizumab have been updated in this section to reflect the Jan.10, 2023 NCI modifications to pembrolizumab dose modification guidelines. The changes are as follows:
- a. [Section 8.3a:](#) The section title has been updated to “Dose Modification and Toxicity Management for Immune-related Adverse Events Associated with Pembrolizumab”. Additional information has been added regarding identification and management of immune-related AEs (irAEs), infusion-reactions, and non-irAEs.
- b. [Section 8.3a, Table 1](#) has been updated as follows:

General instructions

- Instruction 1 has been changed to include non-endocrine-related severe and life-threatening irAEs. A statement has been added to highlight that some non-endocrine irAEs do not require steroids.
- Instruction 2 has been revised to specifically mention non-endocrine-related toxicities.
- Instruction 3 has been reworded for clarity.
- Instruction 4 has been revised to clarify instructions for non-endocrine irAE.

irAEs Toxicity Management Guidelines

- Diarrhea / Colitis:
 - In the "Corticosteroid and/or other therapy" section, a sentence has been added to clarify that a gastroenterologist should examine patients who do not respond to corticosteroids in order to confirm the diagnosis and assess secondary immune suppression.
 - The section "Monitoring and Follow-up" has been updated to include a statement that participants should specifically be evaluated for celiac disease serologically and rule out Clostridium difficile infections. Additionally, wording has been added for assessing mucosal severity for participants with ≥Grade 2.
- Type 1 diabetes mellitus (T1DM) or Hyperglycemia:
 - New guidelines for “Grade 1 or 2” have been added.
 - “New Onset T1DM or Grade 3 or 4 hyperglycemia associated with evidence of B-cell failure” has been updated to “New onset T1DM (evidence of B-cell failure) or Grade 3 or 4 hyperglycemia” and the following have been added: a clarification for resuming pembrolizumab and updates to management, monitoring, and follow-up.

- Hypophysitis:
 - Under the column "Monitoring and follow-up," a statement has been added to instruct patients are to be provided with adrenal insufficiency precautions, including indications for stress dosage steroids and medical alert jewelry, and that they should consider referral to an endocrinologist.
- Hyperthyroidism:
 - For Grade 2, in the column "Action with pembrolizumab", "continue" have been updated to "Consider withholding. Resume pembrolizumab once symptoms have subsided and thyroid function has improved".
 - A sentence has been added under the column "Corticosteroid and/or other medications" to initiate treatment with an anti-thyroid medicine such as methimazole or carbimazole as needed.
 - A sentence has been inserted under the column "Monitoring and follow-up" stating that patients should strongly consider referral to an endocrinologist.
- Nephritis:
 - In the "Monitoring and Follow-up" section, a statement has been added advising patients to strongly consider referral to a nephrologist.
- The "Myocarditis" section have been updated to "Cardiac Events (including myocarditis, pericarditis, arrhythmias, impaired ventricular function, vasculitis)"
 - Grade 1 has been clarified as "Asymptomatic cardiac enzyme elevation with clinical suspicion of myocarditis (previously CTCAE v4.0 Grade 1), or Grade 1" and now has separate guidelines for management, monitoring, and follow-up. Additional guidelines have been added for Grade 1.
 - The guidelines for Grade 2 have been combined with Grades 3-4. Additional guidelines for management, monitoring, and follow-up have been added.
- Guidelines for "Exfoliative Dermatologic Conditions" have been added.
- The footnotes have been updated as follows:
 - Added definitions for acronyms used within the table.
 - Added a note about managing non-irAEs following clinical practice recommendations.
 - The sentence referring to resuscitation equipment and physician availability has also been included here.
- c. [Section 8.3b, Table 2](#): The table title was revised to "Pembrolizumab (MK-3475) Infusion Reaction Treatment Guidelines". The table has been updated as follows:
 - An additional column has been added for "Infusion Reactions" description as it applies to each NCI CTCAE Grade.
 - Under grade 3 treatment, corticosteroids was clarified to include the following additional information " (e.g. methylprednisolone 2 mg/kg/day or dexamethasone 10 mg every 6 hours)"
 - "Grade 4" guidelines have been separated from "Grade 3". Instructions have been added to admit participants to the intensive care unit (ICU) with monitoring and additional treatment and, as appropriate, follow Grade 3 recommendations.
- d. [Section 8.3, Table 3](#): A section has been added for Management of Neurological toxicities and The Neurological Toxicities table has been added to this section. Subsequent sections have been renumbered.

Model Consent Form Changes

1. The version date has been updated.

2. The Pembrolizumab (MK-3475) risk profile date has been updated to CAEPR Version 2.7, December 13, 2022.
3. Possible Side effects of Pembrolizumab (MK-3475) updates:

Deleted Risk Attribution:

- Occasional: Infection

Decreased in Risk Attribution:

- Changed to Also Reported on Pembrolizumab (MK-3475) Trials But With Insufficient Evidence for Attribution from Occasional (i.e., removed from the Risk Profile): Fluid in the joints; Pain in chest
- Provided Further Clarification: Rare: Changed from “Swelling and redness of the eye” to “Swelling and redness of the eye which may cause blurred vision with a chance of blindness”

PLEASE NOTE: The potential risks listed in the CAEPR whose relationship to pembrolizumab is still undetermined are not required by CTEP to be described in the ICD; however, they may be communicated to patients according to local IRB requirements.

Patient Notification and use of Consent Addendum:

Please note that the information provided below regarding patient notification and amendments to local consent forms reflects SWOG’s minimum requirements. Sites should refer to the policies/procedures of the IRB of record to determine whether they have any more stringent requirements

SWOG has determined that the changes above that are **bolded** may affect a patient’s willingness to participate in the study; therefore, SWOG requires that patients be notified of these changes.

Who must be informed?

- All patients currently on study treatment with Pembrolizumab (MK-3475).

How must patients be notified?

- For patients currently receiving Pembrolizumab (MK-3475): Notification must take place either via the attached Consent Addendum or via amended consent form by next study visit. After the change has been discussed with the patient, the patient must sign and date either the Consent Addendum or the 2/15/2023 version of the consent form.

What is the notification deadline and process?

- For patients currently receiving treatment with Pembrolizumab (MK-3475): Patients must be notified by their next scheduled visit or within 90 days after CTSU distribution of this revision, whichever is sooner.
- Sites using the NCI CIRB as their IRB of record: CIRB has approved the attached Consent Addendum; therefore, the Consent Addendum may be utilized immediately to notify patients of these changes.
- Sites not using the NCI CIRB as their IRB of record: If local IRB approval of the Consent Addendum is required before sites may utilize it, the site must still notify patients verbally prior to the notification deadline and notification must be documented in the patient chart. The site must then obtain patient signature on the Consent Addendum or updated consent form once the addendum and/or revised consent is locally approved. Important: Any changes to eligibility criterion are effective 30 days after distribution of this notice. If local IRB approval is not granted within 30 days, new registrations must meet any revised eligibility criteria included in the revision or accrual must be suspended until approval is obtained.

Regulatory Considerations:

Do local consent forms need to be updated?

- It depends. If your site will utilize the updated consent form for notification and formal re-consent then local consent forms must be updated. If your site will not utilize updated consent form for notification and formal re-consent then local consent forms need not be updated.

Can accrual continue until local implementation of the 2/15/2023 version of the consent form?

- Unless otherwise noted in the Action Letter, accrual may continue; however:
 - Patients enrolled after the notification deadline must be enrolled under the 2/15/2023 version of the consent form.
 - Sites using the NCI CIRB as their IRB of record: Patients enrolled prior to the notification deadline but before the 1/30/2023 version is implemented locally may be consented by signing the previous version of the consent form 3/21/2022 together with signing the attached Consent Addendum.

SCHEMA

* Participants on Adjuvant arm must be registered to Step 2 (Surgery) within 17 days (preferably within 14 days) after randomization and must undergo surgical resection within 17 days (preferably within 14 days) after Step 2 registration.

** See [Section 7.1](#) for dosage and timing. Participants must start adjuvant therapy within 84 days of surgery.

1.0 OBJECTIVES

- 1.1 Primary Objective(s)
 - a. To compare event-free survival (EFS) in participants with high-risk resectable melanoma randomized to neoadjuvant pembrolizumab (MK-3475) with participants randomized to adjuvant pembrolizumab (MK-3475).
- 1.2 Secondary Objective(s)
 - a. To assess the frequency and severity of toxicities on each of the arms.
 - b. To compare between arms overall survival (OS), disease control at 24 weeks, locoregional control in the surgical site(s), and total number of pembrolizumab (MK-3475) doses received.
 - c. On the neoadjuvant arm, to estimate the pathologic response rate, the RECIST 1.1 response rate (confirmed and unconfirmed CR and PR), and the iRECIST response rate (confirmed and unconfirmed CR and PR), before surgical resection; to compare definitions of pathologic partial response; and to evaluate the association between pathologic response and EFS and OS.
 - d. To describe the proportion of participants on each arm who received the surgery planned at randomization.
- 1.3 Additional Objective(s)
 - a. To bank tumor tissue and whole blood in anticipation of future correlative studies in this participant population. Such proposed analysis includes deep immune profiling, with evaluation of CD3, CD8, PD-L1, CD20, whole exome sequencing studies, and RNA analysis.

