7.2 Treatment

a. Pre- pembrolizumab (MK-3475) Labs

Blood collected for pretreatment laboratory tests must be collected and analyzed no more than 3 days prior to dosing.

b. Surgery

Participants must undergo surgical resection (lymphadenectomy or resection of in-transit or distant metastasis +/- wide local excision, if applicable) of clinically detectable melanoma. **Timing of surgery is dependent on treatment arm.**

For all participants, the **S1801 Planned Surgery Form** must be filled out prior to randomization and the **S1801 Post-Surgery Form** filled out post-surgery. Submit forms as indicated in [Section 14.0](#).

Pembrolizumab (MK-3475) timing after surgery is up to the discretion of the local investigator. Interval between surgery and start of adjuvant therapy should not exceed 84 days.

c. **Arm 1: Pembrolizumab (MK-3475) Adjuvant Arm**

Step 1: RANDOMIZATION

Participants will be randomized.

Step 2: SURGERY

Participants on Adjuvant arm must be registered to Step 2 (Surgery) within 17 days (preferably within 14 days) after randomization and must undergo surgical resection within 17 days (preferably within 14 days) after Step 2 registration. Radiation is allowed after surgery. **However, interval between Surgery and the start of Adjuvant therapy must not exceed 84 days.**

Step 3: ADJUVANT THERAPY

It is recommended that participants be registered to and initiate treatment on Step 3 (Adjuvant therapy) within 17 days (preferably within 14 days) after surgery. Radiation is allowed after surgery. However, interval between Surgery and start of Adjuvant therapy must not exceed 84 days.

Agent	Dose	Schedule	Route
MK-3475 (pembrolizumab)	200 mg	IV over 30 minutes	Day 1, Q 3 weeks for 18 doses

Pembrolizumab (MK-3475) treatment should be administered after all procedures and assessments have been completed. Pembrolizumab (MK-3475) treatment may be administered up to 3 days before or after the protocol-specified Q 3 weeks due to administrative reasons.

Pembrolizumab (MK-3475) treatment will be administered on an outpatient basis.

Pembrolizumab (MK-3475) will be administered as a 30-minute IV infusion. Infusion timing should be as close to 30 minutes as possible; however, a window of -5 minutes and +10 minutes is permitted (*i.e.*, infusion time is 25-40 minutes).

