10.12 Length of loco-regional control

Measured from date of randomization to date of the first of the following events: progression such that the participant cannot receive protocol surgery, protocol surgery that does not render the participant disease-free, relapse at the primary site and pre-randomization defined regional nodal basins after surgery that did render a participant disease-free; participants last known to be without any of these events will be censored at the date of death or date of recurrence outside of the primary site or pre-randomization defined nodal basin, whichever comes first.

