18.1 Surgical Management Guidelines

a. Excision of the Primary Site

These guidelines apply to participants presenting with an intact primary and planning for a lymph node dissection as their surgical procedure.

Primary Tumor: All such participants must undergo adequate wide excision of the primary tumor meeting the suggested criteria outlined below, if not already completed. In most cases, this must be a wide excision with 1 cm minimum margins. In all cases, the margins of excision must be histologically free of melanoma (including melanoma in-situ or atypical junctional melanocytic hyperplasia). For all sites except head & neck and extremities distal to the wrist or ankle, the primary melanoma must be excised with at least 1 cm margins of normal skin in all directions, measured either from the edge of the primary tumor or from the edge of the biopsy scar if prior excisional biopsy has been done. The excision should go down to the fascia; including the fascia in the resection is optional. Measurements of margins should ideally be done by the surgeon at the time of wide excision using a ruler; if the measurement is done by the pathologist, allowance of 33% for shrinkage will be made. In addition to the gross margin, a histologically negative margin (including histologic freedom from atypical junctional melanocytic hyperplasia) must be obtained.

For primary melanomas on the head & neck or extremities distal to the wrist or ankle, the primary melanoma must be excised and a histologically negative margin (including histologic freedom from atypical junctional melanocytic hyperplasia) must be obtained. Measured margins of at least 1 cm are desirable, but not mandatory. Acral-lentiginous melanomas (including subungual primaries) may be resected by any procedure that yields a histologically negative margin, including amputation and digit-conserving surgery.

b. Excision of Recurrent Disease

All participants enrolled with regional disease, including recurrence after initial presentation, must have clinically detectable, surgically resectable disease (regional or distant disease). Participants presenting with satellite metastases (within 2 cm of the primary) or in transit metastases (beyond 2 cm from the primary but proximal to the regional lymph nodes) are eligible provided that they have been deemed surgically resectable by a surgeon, and they have NOT undergone prohibited systemic therapy for their satellite/in transit metastases (see [Section 5.1b](#)).

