c. Regional Lymph Nodes

Regional lymph node dissection is mandatory for all participants with histologic or clinical evidence of regional lymph node involvement enrolled on this trial. (Participants with satellite/in transit disease and no evidence of nodal involvement may be enrolled without lymph node dissection.) The node dissection must be done in accord with the following guidelines; lymph node sampling is not acceptable. Sentinel lymph node biopsy alone, without completion lymph node dissection, is not acceptable.

The number of tumor-involved nodes must be documented for all cases. Either H&E or immunohistochemical evidence of involvement is acceptable for determining the number of involved nodes, but RT-PCR or other molecular techniques are not. Participants with confluent nodal involvement that makes determination of the exact number of involved nodes difficult are eligible and are considered to have "matted nodes" and classified as N3.

1. Cervical Lymph Node Dissection

A classic radical neck dissection is not required and is discouraged. Preservation of the internal jugular vein, sternocleidomastoid muscle, and eleventh cranial nerve ("functional neck dissection") should be performed whenever possible. Consideration should be given to the parotid gland nodes, particularly for melanomas of the face, anterior ear and temporal region, which should be removed by total parotidectomy if there is evidence of involvement by tumor. The facial nerve (seventh cranial nerve) should be spared unless invaded by tumor.

2. Axillary Lymph Node Dissection

Removal of at least the level I and II axillary lymph nodes is the minimum acceptable operation. Level III nodes must be removed if clinically suspicious. The minimum borders of the dissection are the latissimus dorsi muscle laterally, the axillary vein superiorly, and the medial border of the pectoralis minor muscle medially. The nerves to the serratus anterior (long thoracic nerve) and latissimus dorsi (thoracodorsal nerve) should be identified and preserved if possible. If the primary tumor is on the trunk, consideration should be given to remove the low axillary nodes (at or below the level of the nipple) by following the latissimus dorsi muscle down to its origin on the chest wall and dissecting the node-bearing tissue between it and the serratus anterior muscle.

3. Inguinal or Ilioinguinal Lymph Node Dissection

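### Section 10.12 censors relapse in a resected in-transit bed, although objective 1.2b asks for loco-regional control at the surgical sites

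*Combined protocol and SAP*

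**What the plan says.** Section 1.2, objective b, lists among the between-arm comparisons "locoregional control in the surgical site(s" (the closing bracket falls outside the quote).

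Section 10.12 defines the endpoint as time from randomization to the first of three kinds of event. Two are not tied to a site of relapse: "progression such that the participant cannot receive protocol surgery, protocol surgery that does not render the participant disease-free". The third is "relapse at the primary site and pre-randomization defined regional nodal basins after surgery that did render a participant disease-free". Participants without an event are "censored at the date of death or date of recurrence outside of the primary site or pre-randomization defined nodal basin, whichever comes first".

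Section 7.2b describes protocol surgery as "surgical resection (lymphadenectomy or resection of in-transit or distant metastasis +/- wide local excision, if applicable) of clinically detectable melanoma". Section 18.1b describes "in transit metastases (beyond 2 cm from the primary but proximal to the regional lymph nodes" (again the bracket closes after the quote), and satellites as lying within 2 cm of the primary. Section 18.1c adds: "Participants with satellite/in transit disease and no evidence of nodal involvement may be enrolled without lymph node dissection".

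Section 5.1a admits N1c, N2c, N3c and resectable Stage IV disease. Section 11.4 analyses local/regional control by Kaplan-Meier, log-rank test and Cox model. It offers no version of the endpoint based on the surgical site.

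**The concern.** The objective locates the endpoint by where the surgeon operated. The definition locates it by anatomy, and the two maps differ. An in-transit deposit removed at protocol surgery satisfies both parts of the objective: it is regional disease and it is an operated site. Yet its bed is in neither of the two places where 10.12 counts a relapse.

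This matters for the question the endpoint is there to answer. Section 12.1 sets up a central surgery review because incomplete or lesser surgery after upfront systemic treatment could influence relapse. Regrowth in the operated bed is one of the most direct ways in which that would show. For in-transit disease, 10.12 takes that outcome out of the comparison.

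**Working it through.** No plan figure has to be reproduced. The check is whether any text makes relapse in a resected in-transit bed an event.

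**Step 1: where in-transit disease lies.** Section 18.1b puts it more than 2 cm from the primary and short of the regional nodes. On the protocol's own description it is in neither region that 10.12 names.

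**Step 2: whether it is regional.** The staging table in Section 4.0 has a Stage IIIB row with no nodes, satellite or in-transit metastases present, and M0. Section 18.2 defines N1c in the same way. It is N-category disease, not distant disease.

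**Step 3: whether it is a surgical site.** Section 7.2b makes its resection part of protocol surgery. Section 18.1c lets participants with in-transit disease and no nodal involvement enter without a node dissection. For them the in-transit bed, with wide local excision if applicable, can be the whole operated field. Section 4.0 also allows T0 with no nodes. Such a participant may have no known primary and no involved basin.

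**Step 4: apply 10.12 literally.**

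| First occurrence | Regional disease? | Can be an operated site? | Result under 10.12 |
|---|---|---|---|
| Progression that prevents protocol surgery | any site | not applicable | event |
| Surgery that leaves disease | any site | yes | event |
| Relapse at the primary site | yes | yes | event |
| Relapse in a regional basin defined before randomization | yes | yes | event |
| Relapse in a resected satellite bed, within 2 cm | yes | yes | not stated: event only if read as primary site |
| Relapse in a resected in-transit bed | yes | yes | **censored** |
| Relapse at a resected distant site | no | yes | censored |

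The in-transit row is the only one where both terms of the objective are clearly met and the stated rule clearly censors.

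**Step 5: effect on the analysis.** Suppose d such relapses occur at a time when n participants are at risk. Counted as events, they multiply the Kaplan-Meier estimate by 1 - d/n. Censored, they multiply it by 1. The reported control curve can therefore only be equal to or higher than the curve for control that includes the in-transit bed. The direction of any effect on the between-arm comparison cannot be known in advance.

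**Step 6: size.** With 336 eligible participants (Section 11.3), the number of affected events is 336 x p x r. Here p is the share with a resected in-transit site and r is the proportion of them whose first relapse is confined to that bed. The documents give neither p nor r, so no number follows.

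**Step 7: other endpoints.** Section 10.10 (event-free survival) and Section 10.11 (length of disease control) count relapse after surgery without restriction by site. An in-transit relapse is an event in both. The sample size in Sections 11.2 and 11.3 rests on event-free survival and does not depend on 10.12.

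**The case against.** The strongest defence is that the objective says loco-regional before it says surgical site, and that the title and definition in 10.12 follow the first word. This stands for distant disease. A reader might infer that censoring relapse at a resected lung or visceral metastasis is the same error. The documents do not support that: such a site is operated on but is not loco-regional, and counting it under loco-regional control would create a new contradiction. For Stage IV the wording of 1.2b is at most ambiguous. The defence does not help with in-transit disease, which is regional by the protocol's own staging.

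Three other stronger readings should be resisted.

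- A reader might say that surgical-site failure is reported as control. It is not: the participant is censored at recurrence and leaves the risk set.
- A reader might say that the endpoint can never register failure in these participants. That goes too far. Progression that prevents surgery and surgery that leaves disease count wherever the disease is. Participants with in-transit and nodal disease (N2c, N3c) must have a node dissection under Section 18.1c, and relapse in that basin counts.
- A reader might try to size the loss from the model in Section 11.2. That model describes event-free survival, which also includes deaths and failure to start adjuvant therapy. Section 2.0 says only that distant relapses make up more than half of relapses in Stage III. It gives no loco-regional or in-transit fraction.

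It is also fair that the definition is the same in both arms and that randomization is stratified by stage. This limits imbalance, although Stage IIIB in Section 4.0 combines one-node disease with in-transit-only disease. It does not make the endpoint answer the objective.

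**Conclusion.** The point holds for in-transit disease. Following 10.12 literally gives an answer to a narrower question than 1.2b asks, because relapse in a resected in-transit bed is censored by a stated rule and no other section restores it. For satellites within 2 cm the text does not settle the matter. For resected distant sites the censoring is consistent with a loco-regional endpoint, and only the wording of the objective needs attention.

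The consequence is confined to one secondary endpoint. The primary analysis, its sample size and the disease-control endpoint are untouched. The size within this endpoint is unknown and should not be guessed. The conclusion rests on reading the primary site and the nodal basin in their ordinary sense, so that tissue more than 2 cm from the primary and short of the nodes belongs to neither.

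**What to change.** In Section 10.12, define the relapse event as relapse at any of these sites:

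- the primary site;
- a regional nodal basin defined before randomization;
- a satellite or in-transit site documented before randomization on the Planned Surgery Form and resected at protocol surgery.

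Censor for recurrence only when it lies outside all three. Naming satellites also settles the 2 cm question.

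For resected distant sites, keep them outside this endpoint and reword 1.2b to say so. Alternatively, report surgical-site control including distant sites as a separate supportive analysis. Rewording 1.2b to match the present 10.12 would also remove the mismatch, but it would leave operated regional disease outside an endpoint called loco-regional.

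The change is one sentence in 10.12 and a few words in 1.2b, to be made before the arms are compared on this endpoint. Section 7.2b already requires the Planned Surgery Form before randomization, and Section 14.3d requires a form for sites of progression or relapse. The cost is matching each relapse to the planned-surgery record. The fields of these forms are not shown, so the sponsor should confirm that both identify an in-transit site closely enough to be matched.
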